2.1 ELIGIBILITY CRITERIA

CASE SUBJECT SELECTION

We will recruit incident cases of pathologically confirmed PCa at all stages of the disease that are age 40 to 90 years. Treatment can be surgery or therapy. The following check list will be used to verify eligibility of a case subject.

ELIGIBILITY CHECK LIST - PROSTATE CANCER CASES

NAME_____

DATE_____

DATE OF BIRTH_____

ID# _____

Yes	No	Criteria (ALL MUST BE CHECKED)
		Has been diagnosed with prostate cancer within the last two years
		Pathological diagnosis of prostate cancer made at the local hospital
		pathology department
		Resides in Baltimore City or contiguous metropolitan counties, Anne
		Arundel and Prince George's counties, Eastern Shore, western and northern
		Maryland, or adjacent counties in Pennsylvania, Delaware, Virginia, or the
		Washington Metropolitan area
		Has a residential working phone within his home
		Born in the United States
		Of African-American or Caucasian descent, and age 40 to 90 years
		A non-objection statement by the physician from the hospital where the
		patient was identified, or listed as the treating physician by the tumor
		registry or surgical pathology report, to contact the patient
		Is not currently residing in an institution, such as a prison, nursing home, or
		shelter
		Is not a severely ill patient in the intensive care unit
		Speaks English well enough to be interviewed
		Is able to give informed consent
		Is physically and mentally capable of performing the interview
		Has never been interviewed as a control for this study
		Subject provides informed consent and signs form.
		UnwillingUnavailable

NCI IRB Approval:	October 28, 2004
Protocol Number:	05-C-N021

SELECTION OF POPULATION-BASED CONTROLS

Population-based controls will be identified through the Department of Motor Vehicles (DMV), and matched on age (5-year intervals), gender and race to cases. Recruitment of controls will start concurrently with case accrual, using the age and race frequency distribution of cancer patients in previous years, but recruitment objectives can be re-assessed to ensure a frequency-matched study. We will exclude controls that do not have a listed home phone number. The following check list will be used to verify eligibility of a control subject.

ELIGIBILITY CHECK LIST - POPULATION-BASED CONTROLS

NAME_____

DATE_____

DATE OF BIRTH_____

ID# _____

Yes	No	Criteria (ALL MUST BE CHECKED)
		Resides in Baltimore City or contiguous metropolitan counties, Anne
		Arundel and Prince George's counties, Eastern Shore, western and northern
		Maryland, or adjacent counties in Pennsylvania, Delaware, Virginia, or the
		Washington Metropolitan area
		Has a residential working phone within his home
		Born in the United States
		Of African-American or Caucasian descent, and age 40 to 90 years
		Does not have a personal history of cancer other than basal and non-
		melanomic skin cancer
		Have never had radiation therapy or chemotherapy
		Is not currently residing in an institution, such as a prison, nursing home, or
		shelter
		Speaks English well enough to be interviewed
		Is able to give informed consent
		Is physically and mentally capable of performing the interview
		Has never been interviewed as a control for the study
		Subject provides informed consent and signs form.
		UnwillingUnavailable

2.1.1 INCLUSION CRITERIA

CASES

- 1. Has been diagnosed with PCa within the last two years
- 2. Pathological diagnosis of PCa made
- 3. Must reside in Baltimore City or contiguous metropolitan counties, Anne Arundel and Prince George's counties, Eastern Shore, western and northern Maryland, or adjacent counties in Pennsylvania, Delaware, Virginia, or Washington DC area
- 4. Has a residential working phone within his home
- 5. Was born in the United States
- 6. Of African-American or Caucasian descent, and age 40 to 90 years
- 7. Speaks English well enough to be interviewed
- 8. Is physically and mentally capable of performing the interview
- 9. Never has been interviewed as a control for the study
- 10. A non-objection statement to contact the patient has been obtained from the treating physician at the hospital where the patient was identified, or from the physician who is listed as the treating physician

CONTROLS

- 1. Stratified to match cases by age (5-year intervals), gender and race
- 2. Must reside in Baltimore City or contiguous metropolitan counties, Anne Arundel and Prince George's counties, Eastern Shore, western and northern Maryland, or adjacent counties in Pennsylvania, Delaware, Virginia, or Washington DC area
- 3. Has a residential working phone within his house
- 4. Was born in the United States
- 5. Speaks English well enough to be interviewed
- 6. Is physically and mentally capable of performing the interview
- 7. Never has been interviewed as a control for the study (with our tracking database)

2.1.2 EXCLUSION CRITERIA

CASES

- 1. Severely ill subjects in the intensive care unit (they can be reconsidered after discharge from ICU)
- 2. Currently residing in an institution, such as a prison, nursing home, or shelter
- 3. Patient is unable to give informed consent

CONTROLS

- 1. Personal history of cancer other than basal and non-melanomic skin cancer
- 2. History of radiation therapy or chemotherapy
- 3. Currently residing in an institution such as a prison, nursing home or shelter
- 4. Subject is unable to give informed consent

2.2 RESEARCH ELIGIBILITY EVALUATION

The research eligibility for cases is determined by the inclusion and exclusion criteria (see 2.1.1 and 2.1.2) and a non-objection statement by the physician from the hospital where the patient was identified, or listed as the treating physician by the tumor registry or surgical pathology report. Severely ill subjects are not eligible but can be reconsidered after recovery. Under the protocol, no invasive procedure will be performed. Cases will be asked to participate in an interview session and to donate blood and urine, and if applicable, to donate a surgically removed tumor specimen. We will not apply specific tests to evaluate eligibility. Information regarding the pathological diagnosis of PCa will be obtained from pathology and medical records.

The research eligibility of population-based controls is defined by the inclusion and exclusion criteria (see 2.1.1 and 2.1.2). Eligible subjects must be physically and mentally capable of performing the interview. Under the protocol, no invasive procedures will be performed. Subjects will be asked to participate in an interview session and to donate blood and urine.

2.3 PATIENT REGISTRATION AND TREATMENT RANDOMIZATION

The proposed study is not a clinical investigation but an epidemiological casecontrol study. Subjects will not receive any type of therapy under the protocol. The collection of blood is the only medical procedure that is performed for this protocol. Patient care is not modified by the protocol. Cancer patients will receive their usual care and are asked to donate tumor specimens that are surgically removed as part of their routine treatment.

3 STUDY IMPLEMENTATION

The study will be implemented in two phases. The first phase is conducted as a pilot study to evaluate recruitment procedures. The second phase is the main study that will be closed when the projected 1000 cases and 1000 controls have been enrolled. Participants in the pilot study will count toward the total accrual.

TIME SCHEDULE OF THE STUDY

Month 1	Begin pilot study
Month 13	Review and revise protocol if needed Resubmit to IRB if needed
Month 14	Begin accrual for the study at the projected rate of 80 cases* and 80 population-based controls* per year. Cases with prostatectomy and/or therapy will be eligible
Month 62*	Close enrollment if target accruals are met

* have been increased to 120 cases and 120 controls per year; now projected for 2014/15

NCI IRB Approval:	October 28, 2004
Protocol Number:	05-C-N021

PILOT STUDY (was completed in 2006)

During the 12-month pilot phase, we will recruit about 80 patients who are either African-Americans or Caucasians, and have had a radical prostatectomy and/or therapy. We will also start recruiting controls that match the cases on age (5-year intervals) and race. We will recruit the cases at the 2 participating hospitals.

We will assess the availability of PCa patients, who 1) are willing to participate in the study, 2) are of African-American descent or 3) provide tumor specimens. In this period, we expect to recruit 25 patients who will have a radical prostatectomy as the initial treatment. Approximately half of the patients should be of African-American descent. We will also assess the availability of controls that are eligible for both the lung cancer and the PCa case-control study and frequency-match the PCa cases by age and race.

The criteria that are used to determine if the pilot is successful are 1) the accrual of 80 cases and 80 matched controls, 2) the accrual of about 40 cases who are of African-American descent, and 3) the collection of 25 fresh-frozen tumor specimens. If major modifications are required to improve accrual rates or other aspects of the study, then the pilot study will be extended to address these issues. Otherwise, we will start recruiting for the main study at the projected rate of 80 cases and 80 controls per year.

PERSONNEL

The Principal Investigator, [name], and the NCI Project Officer, [name], both at the Laboratory of Human Carcinogenesis, NCI, will be responsible for the overall monitoring of the study. The associate investigators of the study, who are at Baltimore Veterans Affairs Medical Center and the University of Maryland, support the study with their expertise in pathology and clinical aspects of PCa. The study will be facilitated through a service contract to our laboratory. The contractor is the University of Maryland Pathology Department. The contract supports an established epidemiological infrastructure at the 2 participating hospitals. Contract personnel include a PI for the contract and a case-control supervisor, a nurse and interviewers, staff to collect and process biological specimens, data entry personnel, and a statistician and epidemiologist for data analysis and quality control assessment. [name], a software consultant to the Laboratory of Human Carcinogenesis, will assist with database development and management.

PREVIOUS EXPERIENCE OF THE UNIVERSITY OF MARYLAND CONTRACTOR WITH EPIDEMIOLOGICAL CASE-CONTROL STUDIES

[figure not shown]
The first case-control study conducted by the University of Maryland at Baltimore contractor began in 1986, using the University of Maryland Medical Center and the Baltimore Veterans Affairs Medical Center to recruit cases and hospital-based controls. It was a lung cancer study to investigate the association between genotypes and lung cancer risk. A second, follow-up study was completed in 1998, which was designed to replicate the first study with some minor study modifications. A third study begun in 1999. This lung cancer case-control study had a target accrual of 1,200 subjects, separated into 400

NCI IRB Approval:	October 28, 2004
Protocol Number:	05-C-N021

cases, 400 frequency-matched hospital controls, and 400 frequency-matched populationbased controls. Target recruitment in the lung study has now been changed to 1500 cases and 1500 population-based controls. The aim of this study is to investigate lung cancer risk with respect to gender, race, and inherited susceptibility as it relates to mutagen sensitivity, p53 mutation load, and allele variant genes. Mutagen sensitivity is assayed in blood lymphocytes, and compared between cases and controls. Preliminary results confirm the hypothesis that lung cancer patients are more sensitive to mutagen-induced DNA damage. This study (NCI protocol OH98-C-N027) is scheduled to continue for several more years, as the request for recruitment above target accrual has been approved.

3.1 STUDY DESIGN

We are proposing an epidemiological case-control study in which we collect 1) questionnaire information and 2) blood and urine samples from all subjects, and 3) tumor specimens from cases if available. Additional information for cases will be abstracted from medical and pathology records. The duration of the recruitment phase is 5 years. Research laboratory studies will begin at the end of the recruitment phase. The design of the study is illustrated in Figure 3.

3.1.1 QUESTIONNAIRE

Trained interviewers will administer the questionnaire. The interview will last approximately one hour. The questionnaire assesses prior medical and cancer history, tobacco use, dietary risk factors, current medications, occupational history, medical

NCI IRB Approval:	
Protocol Number:	

October 28, 2004 05-C-N021

history and family medical history, socioeconomic status, anthropometry, and sexual history. The sexual history section is self-administered. This questionnaire is shared with the lung study and contains question relevant to both prostate and lung cancer.

INTERVIEWER TRAINING

The interviewers will receive a procedure manual. They will be trained in how to identify eligible subjects, how to provide informed consent, how to administer and properly complete the questionnaire, how to perform phlebotomy, and how to properly process blood and urine samples. The field supervisor will provide the training. Newly hired interviewers will practice the administration of the questionnaire to office volunteers. Interviewers will then administer the questionnaire and draw blood from subjects under the supervision of the field supervisor, who will provide feedback after the interview.

STEPS TO BE TAKEN IF A PATIENT BECOMES EMOTIONALLY UPSET DURING THE INTERVIEW PROCESS

The University of Maryland contractor will train the interviewers for the event that a subject will become emotionally upset during the interview. Part of this training will focus on the scientific background of the study, i.e., the rationale asking these specific questions. We have found that well-informed interviewers are often able to reassure subjects that the information being sought in the interview is needed for the scientific hypotheses that are under study. The interviewer will then be well prepared to answer questions that relate to the sexual history part on pages 18-20 of the supplemental questionnaire. If a subject continues to show signs of distress during the interview, the interviewer will explain that the subject has the right not to answer a question or section of the questionnaire if the subject does not feel comfortably to do so. Indeed, the questionnaire has a special code to denote that the respondent declined a particular question. The interviewers are trained to handle this with neutrality. If the interview is conducted on the premises of the University of Maryland and the Veteran Affairs Hospital, the interviewer will be able to call for help in the event that the above steps have failed to deal with a distressed subject. We have established a list of contacts. [name], [name], and [name], can be called for immediate help. [name] will accept quick referrals and, if requested, will follow up on the incident in a special appointment with the subject. [name] are psychologists at the University of Maryland School of Medicine. [name] is a counselor for patients who have a sexual dysfunction. [name] is a counselor for cancer patients. In the event that an interview takes place off site, e.g., at a subject's home, and the subject has become distressed, the same contact people will be available by telephone.

The list of contacts is as follows:

- 1) [name] (Psychologist), [contact] or [contact] (pager)
- 2) [name] (Psychologist), [contact]
- 3) [name] (Field Supervisor), [contact]
- 4) [name]. (Project Director), [contact]

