2 ELIGIBILITY ASSESSMENT AND ENROLLMENT

The verification of eligibility and enrollment of subjects will follow the procedures that are outlined below and summarized in the two flow diagrams at the end of the section (Figures 1 and 2). A nurse will assess the eligibility of PCa patients, and an interviewer determines the eligibility of population-based controls. Eligible candidates will be offered an incentive with a monetary value of up to \$75 to participate in the study.

October 28, 2004 05-C-N021

ENROLLMENT OF CASES

Cases will be identified through resources including, but not limited to, daily afternoon visits, or phone calls, to the pathology departments to identify all cases diagnosed that day with PCa. We will also review the weekly lists of scheduled surgeries. We have established active collaborations with the Departments of Pathology and Urology at the University of Maryland and the Baltimore Veterans Affairs Medical Center to maximize our ability for recruitment of new PCa cases.

Case recruitment will follow the new HIPAA regulations ("HIPAA Privacy Rule"). However, to better assess eligibility, we will review medical and pathology records, medical examiner reports, cancer center registries and hospital databases. Our contractor has been granted a HIPAA waiver to perform the aforementioned study activities for our protocol.

We have obtained an agreement with the Departments of Urology and the treating physicians that they will put a note into the medical record of severely ill PCa patients. The note will indicate that we should not contact this patient because of health concerns. If no such note is found in the medical record, we will proceed and contact eligible patients. If a note is found, the interviewer will record the reason for refusal on the eligibility record, in addition to age, race, and family history. Other physicians who see prostate cancer patients will contact us through their staff.

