After the eligibility has been confirmed, a nurse will contact patients to get both informed consent and authorization to obtain, use and disclose protected health information for research. A trained interviewer and phlebotomist will administer the questionnaire to those who consented. After the interview, blood will be collected. The investigators will make every effort to obtain informed consent and administer the questionnaire well in advance of either a scheduled surgery or an alternative treatment such as radiation or hormone therapy. Most of the patients will not be rushed to surgery. The disease is detected by needle biopsy and patients may seek a second or third opinion before they decide on a treatment option. Thus, we will have the opportunity of recruiting most patients weeks or months before either a surgery is scheduled or an alternative treatment will start. It is always at the discretion of the patient to give informed consent on one day but to have the interview or the blood collection on another day that is convenient for him. In the situation where we cannot get access to an eligible patient well in advance of surgery, we will approach the patient up to one day before surgery to seek consent. We will offer to administer the questionnaire and obtain blood after the surgery. However, if the patient wishes to be interviewed and have the blood drawn at the same day when he gives informed consent, we will do so. If we would limit our access to surgery patients because of a longer waiting period where we do not approach eligible cases prior to surgery, it could seriously compromise our ability of collecting the number of fresh-frozen tumor specimens that are needed for our research study.

October 28, 2004 05-C-N021

PROCEDURES

- 1. Interviewer obtains patient's name, location and physician's name
- 2. Interviewer screens medical record for eligibility. If eligible, record age, race and family history. Record reasons for ineligibility. Also record histology of tumor
- 3. Interviewer obtains a non-objection statement from the treating physician to contact the patient. If physician refuses, interviewer records reason for refusal on eligibility record, in addition to age, race, and family history of PCa
- 4. Interviewer contacts case and obtains informed consent and authorization to obtain, use and disclose protected health information for research

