5.1.2 QUESTIONNAIRE DATA

The questionnaire data are entered into the survey database twice with a different data entry person each time. If a discrepancy occurs, a supervisor will verify the correct entry. Prior to entry, all questionnaires are coded and edited using a standardized code for occupation, illness, and medication. When appropriate, we utilize the ICD-9 codes (or further updated codes as they become available in the future). A coder will highlight all sections in a questionnaire that contain either an illogical response or missing data. The highlighted sections will be reviewed by a supervisor, or the Research Study Coordinator where needed. A patient may be re-contacted to clarify an answer or to complete a missing response. The supervisor will also examine the coding of about ten percent of the questionnaires. The questionnaires are then entered into the database and verified by the Epi Info software. A contractor to the University of Maryland developed the Epi Info software is programmed to include range checks, skip patterns, and codes for missing data and don't know answers. If errors are detected, a supervisor will assist with the correction. Monthly reports on coding and editing, data entry and the verification status are prepared and presented at monthly staff meetings and site visits.

NCI IRB Approval:	October 28, 2004
Protocol Number:	05-C-N021

During the study, quality control will consist of data comparisons among interviewers to determine the quantity and quality of information that they have gathered, by evaluating characteristics such as interview duration, number of interview problems reported, number of refusals, distribution of subject answers, and number of missing and incomplete answers. In addition, a small random sample of subjects will be re-contacted to inquire about the interview experience, to note any problems, and to confirm that the interview actually took place. Quality assessment will follow procedures that are already in place for the lung cancer study.

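### Interviewers know case status and the study rationale, and read a case's family history before interviewing him, so questionnaire exposure odds ratios may be biased by differential reporting

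*Protocol*

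**What the plan says.** In Protocol 3.1.1, trained interviewers administer the questionnaire, which covers tobacco, diet, medication, occupation, and medical and family history. Only the sexual history section is completed by the subject himself. The contractor "will train the interviewers for the event that a subject will become emotionally upset during the interview". On the content of that preparation: "Part of this training will focus on the scientific background of the study, i.e., the rationale asking these specific questions". The reason given is that "well-informed interviewers are often able to reassure subjects that the information being sought in the interview is needed for the scientific hypotheses" under study. The text adds: "The interviewer will then be well prepared to answer questions that relate to the sexual history part". If distress continues, the subject is told that he may decline, and a refusal code exists. The instruction to be neutral concerns declined questions.

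Section 2 describes the chart screen in two ways. Its opening says: "A nurse will assess the eligibility of PCa patients, and an interviewer determines the eligibility of population-based controls". Case procedure 2 says: "Interviewer screens medical record for eligibility. If eligible, record age, race and family history"; it also asks for the tumor histology. The control procedures consist of a letter, a phone call, consent and the interview, with no record review.

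On quality control, 5.1.2 says that "quality control will consist of data comparisons among interviewers to determine the quantity and quality of information that they have gathered". It states no comparison by case status. The limitations in 3.1.5 discuss selection, catchment area, confounding disease and accrual, but not interviewer or recall bias.

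**The concern.** Case status can hardly be hidden from an interviewer who meets patients through hospital departments and controls through a driver database. The practical safeguards that remain are to limit what the interviewer knows about the exposures under test and to fix what is said during the interview. Section 3.1.1 teaches the rationale and sets no wording for the reassurance. Procedure 2 then adds an asymmetry: for a case, the interviewer has family history from the chart before asking about it; for a control, he does not.

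The protocol summary's primary hypothesis covers environmental exposures, including infections and medical history, and their interplay with genes. Much of that exposure information comes from interview answers. If cases are probed or recall differently, the resulting association is not removed by adjusting for age, race or other covariates, because the error lies in the exposure variable and depends on the outcome.

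**Working it through.** **What the text establishes**

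| Element | Cases | Controls |
|---|---|---|
| Interviewer knows status | Yes (case procedures, section 2) | Yes: "an interviewer determines the eligibility of population-based controls" |
| Chart seen before interview | Yes under procedure 2; the nurse's task under the opening of section 2 | No such step |
| Rationale training and reassurance | Any subject (3.1.1) | Any subject (3.1.1) |
| Interviewer quality control | Between interviewers | Between interviewers |

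The chart step is the asymmetry that the text itself contains. The reassurance step is worded alike for both groups and becomes differential only if it is used or received differently.

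**Size**

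The protocol gives no reporting accuracy and no share of upset subjects, so there is no figure of its own to reproduce. The calculation below is an illustration.

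Inputs from the protocol: 1000 cases and 1000 controls; two-sided alpha 0.05; exposure prevalence 25% (power section, 5.4.2).

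Assumptions: true odds ratio 1; in controls, sensitivity (Se) 0.80 and specificity (Sp) 0.95; case values as listed.

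Formulas:
- Reported prevalence = Se × 0.25 + (1 − Sp) × 0.75.
- Apparent OR = [p1/(1 − p1)] / [p0/(1 − p0)], with p1 in cases and p0 in controls.
- Rejection probability = Φ((d − 1.96·s0)/s1) + Φ((−d − 1.96·s0)/s1), with d = p1 − p0, s0 = √(2·p̄(1 − p̄)/1000), where p̄ is the mean of p1 and p0, and s1 = √([p1(1 − p1) + p0(1 − p0)]/1000).

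Controls: 0.80 × 0.25 + 0.05 × 0.75 = 0.2375.

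*Shift across all cases*

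| Case Se / Sp | p1 | Apparent OR | Chance of p < 0.05 |
|---|---|---|---|
| 0.80 / 0.95 (no shift) | 0.2375 | 1.00 | 0.05 |
| 0.85 / 0.95 | 0.2500 | 1.07 | 0.10 |
| 0.90 / 0.95 | 0.2625 | 1.14 | 0.25 |
| 0.95 / 0.95 | 0.2750 | 1.22 | 0.48 |
| 0.90 / 0.90 | 0.3000 | 1.38 | 0.88 |

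Example: (0.2625/0.7375)/(0.2375/0.7625) = 0.3559/0.3115 = 1.14.

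A second set of assumptions (20% exposure; controls Se 0.80 and false-positive rate 0.02, so p0 = 0.176) gives similar results. Case Se 0.90 gives p1 = 0.196, OR 1.14 and chance 0.21. With the case false-positive rate also at 0.05, p1 = 0.220, OR 1.32 and chance 0.69.

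*Shift only in upset cases (their Se 0.80 to 0.95, 25% exposure)*

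| Share of cases upset | Average case Se | p1 | Apparent OR | Chance of p < 0.05 |
|---|---|---|---|---|
| 5% | 0.8075 | 0.2394 | 1.01 | 0.051 |
| 10% | 0.8150 | 0.2413 | 1.02 | 0.054 |
| 20% | 0.8300 | 0.2450 | 1.04 | 0.068 |
| 50% | 0.8750 | 0.2563 | 1.11 | 0.163 |

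Reassuring a small upset minority therefore barely moves the odds ratio. A shift that matters would have to come from how interviews are conducted generally by someone who knows both status and rationale.

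**Which results are exposed**

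Genotype main effects come from blood DNA and are untouched. For interaction, suppose that reporting error does not depend on genotype and that genotype and exposure are independent. Carriers and non-carriers then show the same spurious exposure OR, say 1.14, and the ratio 1.14/1.14 = 1 leaves a null multiplicative interaction null. The joint category in Tables 11 and 12 (prevalence 0.20 × 0.25 = 0.05), compared with neither factor, would carry the factor 1.14.

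**The case against.** Several points on the other side are sound.

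- A reader might infer from the distress procedure that exposure reports shift in cases only. The text does not support that. The heading mentions a patient, but the procedure covers any subject, and interviewers also question controls. That cases become upset more often is plausible but documented nowhere.
- A reader might also infer that the reason for each question, or an expected answer, is disclosed. The text says only that the information is needed for the hypotheses.
- The section most likely to cause distress is self-administered, which leaves the interviewer least scope there.
- The study purpose is explained to every case and control at consent (6.5), so respondents are not unaware of it in any event.
- Interviewers receive a procedure manual, which is not shown and may contain neutral probing rules.
- All the spurious odds ratios above lie below 1.5, the smallest association that 5.4.2 aims to detect. The study is called exploratory, with later validation.
- Reassuring distressed men with a reason is reported to work often, and taking it away has a price.

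What remains: status is known, the rationale is taught, no standard reassurance wording is given, and the chart step is one-sided and contradicts the opening of section 2. The 1.5 target was argued mainly for genotypes, and 5.4.3 sets no odds ratio threshold for reporting exposure results. Section 2 names roles, not people, so one person need not both screen the chart and interview the case, but nothing prevents it.

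**Conclusion.** The concern holds as a real, open route to differential reporting of questionnaire exposures. It reaches exposure odds ratios and contrasts that combine genotype and exposure. To read it as threatening the genotype associations, or every interaction test, would go too far: the former do not use interview data, and a null multiplicative interaction stays null under the conditions shown.

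Neither the presence nor the size of a bias can be derived from the protocol. With assumed error rates and no true effect, a shift across all cases gives an apparent OR of about 1.1 to 1.4 and a false-positive chance of 0.10 to 0.88 at 1000/1000. A shift confined to an upset 5% to 20% of cases gives 1.01 to 1.04 and 0.051 to 0.068. The larger figures describe status-dependent interviewing in general and must not be read as the effect of the reassurance step alone. Equal accuracy in both groups gives an OR of 1.00 and 0.05.

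**What to change.** - **3.1.1:** Replace rationale-based reassurance during the interview with one fixed, hypothesis-free statement used alike for cases and controls. Answer questions about the rationale once the questionnaire is complete. The right to decline and the referral contacts stay as they are.
- **Section 2:** Reconcile the opening paragraph with case procedure 2 so that the nurse already named does the case chart screen and the interviewer does not see family history or histology before the interview.
- **5.1.2:** Run the existing interviewer comparison separately within cases and within controls. This can show individual interviewers whose results differ by status; it cannot show a shift shared by all of them.
- **3.1.5:** Name interviewer and recall bias as a limitation of questionnaire exposures.

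The cost is wording in the protocol and interviewer materials, some chart work moved between existing staff, and one further tabulation. Reassurance during the interview becomes less specific, which is a real trade-off for distressed men. Status remains unmasked. Because accrual is under way, the change helps only interviews still to be done; those already completed can only be covered by the stated limitation.
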